3.1 Research Design and Planning

This study is a prospective, single-center clinical trial employing anlotinib combined with sintilimab. Based on preliminary research findings and statistical analysis of prior literature, the planned enrollment number is 37 patients.

3.2 Control

Eligible subjects will receive treatment according to the aforementioned protocol, with historical controls as the reference.

3.3 Selection of Study Population

According to the study protocol definition, all subjects were untreated advanced non-hepatic metastatic colorectal cancer.

3.3.1 Eligibility Criteria

- patients with advanced colorectal adenocarcinoma confirmed by histology or cytology;
- patients without liver metastases and who have explicitly refused chemotherapy;
- those who have not received systematic therapy or have developed metastasis or recurrence 12 months after the end of adjuvant therapy;
- The patient has at least one measurable lesion (according to RECIST 1.1 criteria);

- Patients who had received local radiotherapy at least 3 weeks prior to initial drug therapy were eligible for enrollment; however, RECIST-evaluated lesions must not be within the radiotherapy field.
- The patient must be ≥ 18 years of age;
- The ECOG physical status score was 0-1;
- Life expectancy ≥ 12 weeks;
- Patients must be able to understand and voluntarily sign a written informed consent form;
- Women of childbearing age must have a negative pregnancy test result within 7 days prior to initiating treatment. Both the patient and their spouse must use contraception during the study period.

3.3.2 Exclusion Criteria

- patients who have undergone major surgery or severe trauma within 4 weeks prior to the first dose of the medication;
- patients with hypersensitivity to the components in the study protocol;
- patients who are planning to conceive or who are pregnant;
- patients with brain metastases who cannot accurately describe their condition;
- patients with autoimmune diseases or organ transplants;
- treatment within 2 weeks prior to study;
- Study of planned vaccination with live attenuated vaccines within 4 weeks before study initiation or during the study;
- The patient has received anlotinib or anti-PD-1/PD-L1 monoclonal antibody therapy, or other treatments targeting T-cell co-stimulatory targets or checkpoints.
- Within 6 months prior to the initiation of the study, the following conditions were present: myocardial infarction (MI), severe/unstable angina pectoris, NYHA class 2 or higher congestive heart failure, poorly controlled arrhythmias, etc.
- Abnormal laboratory test results:

-Absolute neutrophil count (ANC) $<1,500/\text{mm}^3$;

-Platelet count $<75,000/\text{mm}^3$;

Total bilirubin>1.5 times the upper limit of normal
Alanine aminotransferase (ALT) and aspartate aminotransferase (AST)>2.5 times the upper limit of normal;
-Creatinine>1.5 times the upper limit of normal;

- Patients with other cancers (excluding advanced colorectal cancer) within five years prior to the initiation of treatment in this study. Excluded: cervical carcinoma in situ, cured basal cell carcinoma, and bladder epithelial tumors.
- Patients with operable colorectal cancer (those who explicitly refuse surgery or are unsuitable for surgery may be enrolled);
- history of drug abuse, substance use, or alcohol dependence;
- lack of legal capacity or limited civil capacity;
- Other circumstances deemed unsuitable for enrollment by the investigators.

3.4 Study Duration

Based on an estimated enrollment of approximately 5 patients per month, the enrollment period would require approximately 8 months. The total study duration is estimated to be around 12 months.

3.5 Subject Withdrawal from the Study

Discontinued cases refer to patients who cease medication for various reasons during clinical studies. Patients meeting the following criteria will be withdrawn from the study:

- The patient or their legal representative requests withdrawal;
- According to the investigators 'opinion, continued participation in the study would be harmful to the patient's health.
- patients with severe non-adherence or serious protocol violations;
- The patient is pregnant, and pregnancy should be reported as a serious adverse event.
- When other diseases occur concurrently during the study, and based on the investigator's assessment that the disease will significantly affect the evaluation of the patient's clinical condition, and when discontinuation of the current treatment regimen is required;
- other malignancies requiring treatment;
- lost to follow-up;

- Use of prohibited drugs or other drugs that the investigator judges may cause toxic reactions or bias the results of the study;
- The patient died.

All patients who withdraw from the study should have the reason for withdrawal recorded in the case report form and the patient's medical record.

All patients who withdrew due to adverse events or abnormal laboratory findings should be followed up until the adverse event resolved or stabilized, with subsequent outcomes recorded. If a patient died during the trial or within 30 days after trial completion, the investigator must be notified by the researchers. The cause of death must be documented in detail on the Serious Adverse Event (SAE) report form within 24 hours.

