3.6.2.1 Dose Adjustment

During the treatment phase of this study, the dose of the relevant drug should be

reduced or the medication should be suspended if any of the drug-induced severe toxic reactions occurs.

The dose adjustment for the next cycle will be based on the toxic reactions observed in the previous cycle.

In the event of any severe hypersensitivity reaction to the relevant medication during treatment, the injection should be immediately discontinued and documented.

If a patient develops a severe hypersensitivity reaction on day 1 of the first treatment course, the patient should be excluded from the study.

Imaging evaluation should be performed even if the patient has developed hypersensitivity to the drug, provided that at least two cycles of chemotherapy have been completed.

The specific dose adjustment was implemented according to the chemotherapy-related adverse event management guidelines and drug instructions.

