3.6.4 Treatment Compliance

The dosage and administration time of each medication used in each treatment course for every subject should be recorded in the CRF form. Reasons for delayed administration, dose reduction, or missed doses should also be documented in the CRF.

Subject compliance with treatment and protocol includes voluntary adherence to all aspects of the protocol, including compliance with all blood draws required for safety assessment. Subjects who fail to return for follow-up visits or administer medications on time may be excluded from the study based on the opinion of the principal investigator or sponsor.

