3.7.3.1 Research Visits

- Screening visit should be conducted within 28 days prior to initiation of study drug therapy.
- The treatment period refers to the duration from the initiation of the first study drug administration until the patient discontinues the study drug therapy.
- Patients were evaluated every 8 weeks after discontinuation of study drug therapy due to non-progressive conditions. If disease progression was confirmed, they would enter the follow-up period. During this period, contact with patients should be maintained every 3 months until the patient's death was recorded, to collect data on overall survival.

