Efficacy Evaluation: All patients will undergo one of the following efficacy evaluations:

Complete remission (CR): All clinical and imaging evidence of the tumor (including target and non-target lesions) is eliminated.

Partial response (PR): A reduction of at least 30% in the sum of LD values at the target lesion compared to baseline total LD.

Stable Disease (SD): A stable state of the disease. The lesion has not met the PR criteria for shrinkage or has not met the PD criteria for progression.

Disease progression (PD): Referring to the minimum total LD value recorded from the start of treatment, the sum of LD in the measured lesions increases by at least 20% or one or more new lesions appear. The emergence of any new lesions indicates disease progression. In special cases, unmeasurable lesions with clear progression may also be accepted as evidence of disease progression.

Evaluation of therapeutic efficacy for target lesions versus non-target lesions

Target lesion	Non-target lesions	New lesion	Overall response	This type of optimal response also requires
CR	CR	not have	CR	Confirm after 4 weeks
CR	Non-CR/Non-PD	not have	PR	Confirm after 4 weeks
PR	Non-PD	not have	PR	
SD	Non-PD	not have	SD	At least 4 weeks from the baseline period
PD	any	Present or absent	PD	No SD, PR, or CR had occurred previously.
any	PD	Present or absent	PD	

any	any	have	PD	
-----	-----	------	----	--

Patients with an overall deterioration in health status requiring treatment discontinuation should be reported as 'symptom exacerbation' if there is no objective evidence of disease progression at this time. Objective disease progression should be observed and documented as closely as possible even after treatment cessation.

Relief time

The duration of remission should be calculated from the time of the first meeting of the criteria for CR or PR (whichever is recorded first) until the date of the first recorded disease recurrence or progression.

disease stable time

The duration of disease stability should be calculated from the start of treatment until disease progression is achieved, with the minimum measured lesion size after treatment initiation serving as the reference.

measuring method

The same evaluation criteria and measurement techniques should be used to describe and report each designated lesion during both the baseline and follow-up periods.

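### Section 3.5 does not separate stopping study treatment from leaving the study, so withdrawn or excluded patients may drop out of PFS and OS follow-up

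*Protocol*

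**What the plan says.** Under the heading on subject withdrawal, Protocol section 3.5 begins: "Discontinued cases refer to patients who cease medication for various reasons during clinical studies". The next sentence is "Patients meeting the following criteria will be withdrawn from the study", followed by a list that the synopsis repeats as exit criteria. Some items are reasons for stopping treatment: the investigator's opinion that "continued participation in the study would be harmful to the patient's health", severe non-adherence, concurrent disease "when discontinuation of the current treatment regimen is required", another malignancy, and prohibited or potentially biasing drugs. Others end observation by their nature: loss to follow-up and death. A patient's request is listed without saying whether it concerns treatment or follow-up.

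After withdrawal, 3.5 asks for the reason to be recorded. Patients withdrawn for adverse events or laboratory findings are followed until the event resolves or stabilizes, with later outcomes recorded. Tumour assessment and survival contact are not mentioned.

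Two other sections remove patients from the study. Section 3.6.2.1: "If a patient develops a severe hypersensitivity reaction on day 1 of the first treatment course, the patient should be excluded from the study". Section 3.6.4: those who miss visits or do not take medication on time "may be excluded from the study based on the opinion of the principal investigator or sponsor".

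Against this stand the follow-up rules. Section 3.7.3.1: "Patients were evaluated every 8 weeks after discontinuation of study drug therapy due to non-progressive conditions", moving on confirmed progression to 3-monthly contact until death. Section 3.8.5 repeats the survival contact. Section 7.3, on patients who stop for deterioration without documented progression: "Objective disease progression should be observed and documented as closely as possible even after treatment cessation".

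**The concern.** A patient stopped for investigator-judged harm or concurrent disease fits two sets of rules: withdrawal under 3.5, and evaluation after non-progressive discontinuation under 3.7.3.1. A site cannot tell which applies.

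The survival contacts are also at risk. In 3.7.3.1 and 3.8.5 they start after progression, so a patient who leaves tumour evaluation before progression never reaches the event that starts them.

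Investigator-judged harm, serious concurrent disease, a second malignancy and missed visits may all be related to prognosis. If follow-up ends there, the patient is censored at a time connected with a coming event, and Kaplan-Meier estimates of PFS and OS are biased upward. There is no concurrent arm to share the bias, since section 3.2 names historical controls as the reference. Investigators also assess response and progression themselves, so removal at the opinion of the principal investigator or sponsor can follow knowledge of how the patient is doing. An analysis plan cannot recover visits that were not made.

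**Working it through.** **1. The plan's own figure.** The sample size of 37 rests on ORR 50% versus 70%, one-sided alpha 0.05 and power 0.80 (synopsis). Exact enumeration of Simon two-stage designs gives the minimax design n1 = 23, r1 = 12, N = 37, r = 23, with alpha 0.0482 and power 0.8011. The figure reproduces, and this point does not touch it.

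**2. The passages side by side.**

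| Situation | Rule that removes | Rule that follows |
|---|---|---|
| Investigator judges participation harmful | 3.5: withdrawn | 3.7.3.1: every 8 weeks, then survival contact |
| Concurrent disease, regimen stopped | 3.5: withdrawn | 3.7.3.1, as above |
| Deterioration without a progression scan | 3.5, only if the harm item is invoked | 7.3: document progression (silent on survival) |
| Day-1 severe hypersensitivity | 3.6.2.1: excluded; imaging after hypersensitivity is tied to two completed cycles | 3.7.3.1, if read as a non-progressive stop |
| Missed visits or late medication | 3.6.4: may be excluded | none specific |
| Progression | flowchart footnote 4 speaks of withdrawal from the study | 3.8.5 and flowchart: contact every 3 months |

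No passage says that withdrawn or excluded patients leave PFS and OS follow-up, and none says that they stay.

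**3. The off-treatment rules also conflict.** After a non-progressive stop, 3.7.3.1 and the flowchart say every 8 weeks and 3.8.3 says every 3 months. After progression, 3.7.3.1 and 3.8.5 say until death, and flowchart footnote 9 says until 1 year after progression or death.

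**4. Illustration of size.** Input: median PFS 14.9 months, the earlier study's figure for patients without liver metastases (Introduction). Everything else is assumed: exponential times, and no other censoring.

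(a) If a fraction f of events is lost at random because the patient is withdrawn just before the event, the observed hazard is (1 − f) times the true one, so the median becomes 14.9/(1 − f):
- f = 5%: 14.9/0.95 = 15.7 months
- f = 15%: 14.9/0.85 = 17.5 months
- f = 25%: 14.9/0.75 = 19.9 months

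(b) A simulation of 200,000 patients censored those withdrawn at half their true event time. The withdrawn were either a random sample or all drawn from patients who would progress within 9 months, a share of 1 − 0.5^(9/14.9) = 34% of all patients.

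| Withdrawn | Median, random | Median, early progressors | 12-month PFS, random | 12-month PFS, early progressors |
|---|---|---|---|---|
| 0% | 14.8 | 14.8 | 57.1% | 57.1% |
| 5% | 15.4 | 16.0 | 58.4% | 60.4% |
| 10% | 16.0 | 17.3 | 59.7% | 64.0% |
| 20% | 17.3 | 19.9 | 62.4% | 72.2% |

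The exact 12-month value without withdrawal is 0.5^(12/14.9) = 57.2%. Of 37 patients, 5%, 10% and 20% are about 2, 4 and 7. Even the random rows are biased, because the censoring time is tied to the event time. If withdrawal were unrelated to the coming event, Kaplan-Meier would lose only precision.

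The 12-month column is the more useful one. From December 2025 to the end of analysis in June 2027 (synopsis), follow-up cannot exceed about 18 months, so a median of 19.9 months could not be observed at that analysis.

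**The case against.** The strongest reply is that the protocol already provides follow-up off treatment and merely uses its words loosely. Section 3.5 opens with stopping medication. Flowchart footnote 4 speaks of withdrawal from the study at progression, yet the same flowchart has a follow-up column after progression. So the phrase is used at least once for patients who remain in survival follow-up. On that usage withdrawal means end of treatment, and 3.7.3.1, 3.8.3 and 3.8.5 govern what comes next.

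This stands in part. It rules out three stronger readings that a reader might infer:
- **That follow-up does end and the data are never collected.** The protocol is silent; loss is a risk of the literal reading.
- **That every stop of medication is a withdrawal.** Progression and intolerance, the stopping reasons in 3.6.1, are not items in the 3.5 list. Clinical deterioration is not one either, so the overlap with 7.3 arises only through the harm item.
- **That those removed are poor-prognosis patients in general.** Pregnancy, patient request and day-1 hypersensitivity are not in themselves markers of prognosis.

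The reply does not remove the point. The 3.5 list also holds loss to follow-up and death, which do end observation, so the mild meaning cannot be applied throughout. Exclusion from the study in 3.6.2.1 and 3.6.4 is harder still to read as end of treatment only.

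**Conclusion.** The point holds as an unresolved conflict between sections. The protocol does not separate stopping study treatment from leaving the study, and does not say whether withdrawn or excluded patients stay in tumour and survival follow-up. Informative censoring of PFS and OS is therefore possible, and on the assumptions shown its direction is upward.

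Its size cannot be derived. The protocol gives no withdrawal rate, and the illustration depends on the assumed rates, on exponential times and on withdrawal occurring ahead of the event. It shows that a handful of such patients among 37 could move 12-month PFS by anything from about 1 to 15 percentage points. It does not predict that this will happen. No figure was derived for OS.

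The ORR sample size stands. Section 5.1.1 separately limits the efficacy population to patients with at least two cycles, so follow-up alone would not bring a day-1 exclusion into the PFS and OS analysis. That is a different point.

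**What to change.** Amend 3.5, the synopsis exit criteria, 3.6.2.1, 3.6.4 and flowchart footnote 4 so that they distinguish two things:

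- **Discontinuation of study treatment.** These patients stay in survival follow-up and, where clinically appropriate, in tumour assessment until progression.
- **End of study participation.** Limit this to withdrawal of consent to follow-up, loss to follow-up and death. For a patient's request, record whether it concerns treatment, follow-up or both.

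In the same amendment, reconcile the interval after a non-progressive stop (8 weeks in 3.7.3.1 and the flowchart, 3 months in 3.8.3), the length of follow-up after progression (until death, or 1 year in footnote 9), and the two-cycle condition on imaging after hypersensitivity in 3.6.2.1. State that survival contact also applies to patients who stop before progression.

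When treatment stops, and how pregnant patients are imaged, stays with the clinical sections.

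The cost is wording in five places, the schedule reconciliation, and a few more contacts per discontinued patient. The visits and 3-monthly contacts already exist in the protocol.

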3.6 Treatment Plan

3.6.1 Treatment Arrangements

Treatment regimen: Anlotinib, orally, 12 mg once daily, administered from day 1 to day 14 of each cycle, with each cycle lasting 3 weeks; Sintilimab, 200 mg, intravenous infusion for 1 hour \pm 5 minutes, administered every 3 weeks until disease progression or intolerable adverse reactions occur.

Treatment should be continued until disease progression or intolerance is achieved. Due to the inherent limitations of the RECIST criteria used for efficacy evaluation, if imaging suggests disease progression but the study physician determines that the patient has clinical benefit, treatment may still be continued.

The efficacy was evaluated every 6 weeks.

3.6.2 Delay in Drug Administration and Dose Adjustment

Patients' toxic reactions should be closely monitored, and dosage adjustments should be made based on their tolerance. It is recommended to adjust the dosage according to the most severe toxic reaction or laboratory abnormalities observed during the previous treatment course or the current treatment course. The severity of toxic reactions should be graded according to NCI CTC AE 5.0. If multiple toxic reactions occur, the dosage should be adjusted based on the most severe toxic reaction.

Medication may be reduced or suspended at any stage of the study due to adverse events.

All adverse events should be graded according to the criteria of NCI CTCAE 5.0.

3.6.2.1 Dose Adjustment

During the treatment phase of this study, the dose of the relevant drug should be

reduced or the medication should be suspended if any of the drug-induced severe toxic reactions occurs.

The dose adjustment for the next cycle will be based on the toxic reactions observed in the previous cycle.

In the event of any severe hypersensitivity reaction to the relevant medication during treatment, the injection should be immediately discontinued and documented.

If a patient develops a severe hypersensitivity reaction on day 1 of the first treatment course, the patient should be excluded from the study.

Imaging evaluation should be performed even if the patient has developed hypersensitivity to the drug, provided that at least two cycles of chemotherapy have been completed.

The specific dose adjustment was implemented according to the chemotherapy-related adverse event management guidelines and drug instructions.

3.6.3 Adjunctive Therapy

3.6.3.1 Therapies Not Permitted

- No other anticancer drug therapy is permitted except for the prescribed treatment regimen.
- Experimental drugs (e.g. experimental antibiotics, antiemetics, etc.)
- Any herbal medicine with antitumor indication during the treatment process.
- Radiotherapy, excluding palliative radiotherapy for existing bone metastases.

3.6.3.2 Permitted Therapies

- Unconventional therapies (e.g., non-cancer-related herbal treatments or acupuncture) and vitamins/microelements may also be administered at the discretion of the investigator, provided they do not interfere with the observation of the study endpoint.
- Patients may receive palliative and supportive care for their underlying condition, such as bisphosphonate therapy.
- Radiation therapy for existing bone lesions (bone metastases present at baseline) with the aim of symptom relief.
- Patients with known bone metastases at baseline who require radiotherapy should complete radiotherapy prior to the first administration of the investigational drug.

- Patients with pre-existing bone metastases at baseline who did not require radiotherapy prior to the first administration of the investigational drug but subsequently required radiotherapy during the study were permitted to receive radiotherapy.
- Patients who received radiotherapy for bone metastases at baseline and require subsequent radiotherapy during the study may undergo additional radiation therapy.
- Topical corticosteroids for the treatment of rash or cutaneous reactions of the hands and feet.

3.6.4 Treatment Compliance

The dosage and administration time of each medication used in each treatment course for every subject should be recorded in the CRF form. Reasons for delayed administration, dose reduction, or missed doses should also be documented in the CRF.

Subject compliance with treatment and protocol includes voluntary adherence to all aspects of the protocol, including compliance with all blood draws required for safety assessment. Subjects who fail to return for follow-up visits or administer medications on time may be excluded from the study based on the opinion of the principal investigator or sponsor.

